### 11.3 Analysis of Secondary Endpoints

Secondary endpoints include overall survival (OS), event-free survival (EFS), metabolic complete response (CR) rate, safety and tolerability.

A key secondary endpoint for the study is OS. Based on previous data, the estimated 2-year OS in the control arm (Arm 2) was 96%. We assume that overall survival in the experimental arm (Arm 1) will follow an exponential distribution, with 4 years of accrual, 2 additional years of follow-up, a stratified log-rank test at two-sided alpha level of .05 will have 90% power to detect a hazard ratio of 2.8 (corresponds to an improvement of OS from 96% in the control arm (Arm 2) to 98.5% in the experimental arm (Arm 1)). A total of 61 OS events (deaths) are required for the final analysis.

Event free survival (EFS) will be estimated using Kaplan-Meier method and compared between treatment arms using cox regression model. Based on the estimated 2-year modified PFS of 82% in the control arm (Arm 2), and the average hazard ratio 1.54, we anticipate at least 195 events under the alternative hypothesis. With 940 eligible patients, the hazard ratio can be estimated to within  $\pm 0.28$  (95% confidence).

Metabolic complete response is defined using 2014 Lugano classification. In the previous study, the CR rate was 86% at the end of frontline therapy for BV-AVD, but the estimate might include BEACOPP and/or radiation therapy. We assume that the CR rate is 83% for BV-AVD alone, with 940 eligible patients, a binomial test at one-sided alpha level of .025 will have 92% power to detect an increase in CR rate from 83% in the control arm (Arm 2) to 90% in the experimental arm (Arm 1).

Toxicity will be evaluated using the CTCAE Version 5 items. Eligible patients receiving at least one dose of drug will be included in the assessment of adverse events by treatment arms. The maximum Grade for each toxicity will be recorded for each patient, and frequency tables will be reviewed to determine toxicity patterns. With 470 eligible patients in each arm, any toxicity with at least 4% prevalence has at least a 90% chance of occurring within an arm. Toxicity rates in each arm can be estimated to within at least  $\pm 4.5\%$  with 95% confidence. Treatment-related toxicities between arms will be compared using Fisher's exact test stratified by age groups.

Targeted patient-reported toxicities also will be collected at each time point (see [Sections 9.1](#) and [9.2](#)), using the PRO-CTCAE for patients 18 years and older and from youth 12-17 years, using the Ped PRO-CTCAE.

Safety Monitoring: The CTEP IDB Drug Monitor, **S1826** study chairs, statisticians and data coordinator(s) will review aggregate adverse event rates by arms on a monthly basis, and serious adverse events immediately after receiving notification. Additionally, special summary reports will be run more frequently to evaluate adverse events in both arms for the first six weeks of the treatment regimen to ensure that there is no significant increase in adverse events in the combination arm of chemotherapy and immunotherapy. Conference calls will be scheduled to discuss these data as needed.

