### 5.2 Age criteria: Patients must be $\geq$ 12 years of age.

### 5.3 Prior/Concurrent Therapy Criteria

- a. Patients must not have received any prior chemotherapy, radiation, or antibody-based treatment for classical Hodgkin lymphoma. Steroid pre-treatment is permitted as outlined in [Section 5.4k](#)
- b. Patients must not have had prior solid organ transplant.
- c. Patients must not have had prior allogeneic stem cell transplantation.
- d. Patients must not have received a live vaccine within 30 days prior to planned Day 1 of protocol therapy (e.g. measles, mumps, rubella, varicella, yellow fever, rabies, BCG, oral polio vaccine, and oral typhoid).

e. At registration, investigator must declare intent-to-treat with Residual PET Radiation Therapy (Residual PET RT- RPRT) to be administered after patient completes 6 cycles of therapy if, after end of treatment, the patient meets criteria specified in [Section 7.5](#) for receiving RT). Patients will be stratified by investigator's intent-to-treat with Residual PET RT.

- All pediatric patients (< 18 years of age) will be considered intent-to-treat with Residual PET RT at time of registration.

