### 6.0 STRATIFICATION FACTORS

Patients will be randomized between Arm 1 – nivolumab + AVD and Arm 2 – brentuximab vedotin + AVD in a 1:1 fashion using a randomized dynamic balancing algorithm with stratification based on:

- a. Age (years): age 12-17 vs. age 18-60 vs. age > 60
- b. International prognostic score: 0-3 vs. 4-7
- c. Pre-specified plan to use Residual PET Radiation Therapy (Residual PET RT)\*: yes vs. no  
\* See [Section 7.5](#).

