#### 11.2 Interim Analysis

For early reporting, interim analyses will be conducted when 25%, 50% and 75% of anticipated progressions or deaths in the pooled across arms have been observed. This under the alternative hypothesis this approximately corresponds to 58%, 85% of accrual and six months after completing full accrual. Evidence suggesting early termination for of the study would be if the alternative hypothesis of a greater than average hazard ratio control vs. experimental hazard ratio of 1.58 is rejected at a one-sided .5% level at the first interim analysis, and 1% level at second or later of the interim analyses. At the second interim analysis testing would approximately correspond to observing a hazard ratio favoring the control of approximately .96. The conservative first interim analysis acknowledges the potential late therapeutic effect of the experimental arm relative to the control arm. The timing of interim analyses will be based the combined number of PFS events across arms. At full information or the time of primary analysis will occur when 179 PFS events have been observed.

Interim Analysis	Information	One-sided Futility p-value	One-sided superiority P-value
1	25%	.002	NA
2	50%	.01	.005
3	75%	.01	.005

At the second two interim analyses superiority testing will be conducted at the .5% level.

Final Analysis Plan: If the trial is not stopped early, the final analysis will test the null hypothesis ( $HR=1$ ) for PFS using stratified log-rank test with a one-sided alpha of 0.021. The strata used in the stratified log-rank test are those defined and coded as in Section 6.0 in the dynamic balancing randomization scheme utilized for the study. The variables include: Age (years): age 12-17 vs. age 18-60 vs. age > 60, International prognostic score: 0-3 vs. 4-7 and Pre-specified plan to use Residual PET Radiation Therapy (Residual PET RT)\*: yes vs. no. The analysis will be based on modified intent-to-treat and will include all eligible patients as randomized regardless of treatment received. The one-sided alpha of .021 will control of the overall type-one error of the study (including the 2 interim superiority analyses) to be less than .025. The final analysis type-1 error calculations were based simulation studies using the information times specified in the interim analysis schedule and interim analysis specified superiority p-value testing.

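### Section 11.3 does not carry the randomisation factors into the EFS and CR comparisons, and does not say how Fisher's test is combined over age groups: a small loss that wording can remove

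*Combined protocol and SAP*

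**What the plan says.** Section 6.0 allocates patients "in a 1:1 fashion using a randomized dynamic balancing algorithm with stratification based on" age (12-17, 18-60, over 60), IPS (0-3, 4-7) and planned residual PET RT (yes, no). Section 5.3e adds that all patients under 18 "will be considered intent-to-treat with Residual PET RT at time of registration".

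The analyses use these factors unevenly:

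- **PFS** (Section 11.2): the final analysis tests the null hypothesis "for PFS using stratified log-rank test with a one-sided alpha of 0.021", and "The strata used in the stratified log-rank test are those defined and coded as in Section 6.0".
- **OS** (Section 11.3): a stratified log-rank test, with the strata not listed.
- **Quality of life** (Section 18.2g): linear regression adjusted for the stratification factors and the baseline score.
- **EFS** (Section 11.3): "Event free survival (EFS) will be estimated using Kaplan-Meier method and compared between treatment arms using cox regression model". No strata or covariates are named.
- **CR** (Section 11.3): the only method appears in the power statement, "a binomial test at one-sided alpha level of .025 will have 92% power". No strata are named.
- **Toxicity** (Section 11.3): Fisher's "exact test stratified by age groups". Objective 1.2d also asks for a comparison between arms stratified by age group. No method of combining the age groups is given.

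**The concern.** When randomisation is balanced on prognostic factors and the analysis ignores them, the test stays valid. However, its standard error is somewhat too large for arms that are in fact balanced, and a Cox hazard ratio is pulled slightly towards 1. The result is a little less power and a slightly smaller estimated effect.

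EFS is the endpoint where consistency with PFS matters most. Under Section 10.5 it counts non-protocol systemic therapy and non-protocol radiotherapy given without formal progression. Section 7.4b.2 says that a switch of this kind after interim PET in Arm 2 is not a PFS event. EFS is therefore the natural cross-check on PFS in an open-label trial. If PFS is stratified and EFS is not, a difference between the two results mixes endpoint definition with analysis method. An unspecified Cox model also leaves the choice of covariates open until after the data are seen.

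For toxicity, Section 11.3 can be read as three separate tests, one per age group. That reading would give no overall comparison of the arms and would leave each test with little power.

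**Working it through.** **1. The plan's own figures**

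- EFS precision. With 195 events and 1:1 allocation, the 95% half-width for the log hazard ratio is 1.96 × 2/√195 = 0.281. The stated ±0.28 reproduces on the log scale, giving about 1.16 to 2.04 around 1.54. The formula uses no stratum information.
- CR power, 83% v 90%, 470 per arm, one-sided 0.025. The null SE is √(2 × 0.865 × 0.135/470) = 0.02229 and the alternative SE is √((0.83 × 0.17 + 0.90 × 0.10)/470) = 0.02217. Then (0.07 − 1.96 × 0.02229)/0.02217 = 1.19, which is 88.2% power. The stated 92% does not reproduce. That is a separate matter, and the small gains from stratifying in step 3 do not explain it.

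**2. Number of cells**

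Three factors give 3 × 2 × 2 = 12 nominal combinations. All patients under 18 are RT-intent yes, which removes 2 and leaves 10 attainable.

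**3. Effect of ignoring the factors**

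The documents give neither stratum sizes nor prognostic strengths, so these results are illustrative. Inputs from the plan: 940 patients, about 195 EFS events, EFS hazard ratio 1.54, CR 83% v 90%. Assumed: eight strata of assumed size, arms balanced within strata, one-sided 0.025, 3,000 runs per setting. SD is the between-stratum standard deviation on the log-hazard scale (EFS) or log-odds scale (CR). The log-rank test stands in for the Cox comparison.

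| SD | EFS power, unstratified v stratified | CR power, pooled v CMH |
|---|---|---|
| 0 | 84.6% v 84.4% | 88.2% v 88.2% |
| 0.4 | 82.1% v 82.6% | 88.9% v 89.1% |
| 0.8 | 79.2% v 84.3% | 89.5% v 90.1% |

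Under the null, rejection rates for all four tests lay between 0.019 and 0.030. The simulation SE is √(0.025 × 0.975/3,000) ≈ 0.003, so there is no clear inflation.

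A second simulation assumed hazard ratios of 2-4 for age over 60 and 1.5-2 for IPS 4-7, with 1.54 taken as the within-stratum EFS effect. Stratifying gained 0.7 to 2.5 points for EFS (78.0 v 78.7%, 84.7 v 85.8%, 84.1 v 86.6%) and 0.4 to 1.0 points for CR. The unstratified hazard ratio averaged 1.50-1.52. On the log scale that is a shift of ln(1.54/1.52) = 0.013 to ln(1.54/1.50) = 0.026, against the stated precision of 0.28.

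**4. Toxicity**

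Section 2.9 plans 317 + 27 = 344 paediatric patients out of 987, so 344/987 × 470 ≈ 164 per arm. The split of the other 306 into 259 (18-60) and 47 (over 60) is assumed. For 15% v 10% at two-sided 0.05:

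- Separate Fisher tests: 23%, 36% and 5% power for 12-17, 18-60 and over 60.
- One age-stratified CMH test: 64%, or 60% with continuity correction.
- One age-stratified exact conditional test: about 60-61%.
- One Fisher test on the pooled table: 61%.

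**The case against.** Section 11.3 never calls the EFS or CR analysis unstratified. A Cox model can carry strata, and the binomial test appears only in a power statement. This stands: the text is silent, and a reader should not infer that an unstratified analysis was deliberately chosen. But stratification is written out for PFS and OS and adjustment for quality of life, so the plain reading of silence for EFS and CR is no adjustment, and the text needs completing either way.

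The size is small, and this also stands. EFS has no stated alpha or power, so points of power only illustrate the loss. The prognostic inputs are assumed. Section 2.8 reports that high IPS was not significantly associated with progression in S0816, and with no prognostic effect the gain is nil.

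A reader might infer that EFS must estimate the same conditional effect as PFS. The documents do not support that: Section 11.2 specifies a stratified test for PFS and no stratified hazard ratio, and both 1.58 for PFS and 1.54 for EFS are described as average hazard ratios. Taking 1.54 as a within-stratum effect is an assumption of the second simulation.

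On toxicity, a reader might infer that Fisher's test has no stratified form and that most of the power is lost. The exact conditional test with a common odds ratio is the stratified extension of Fisher's test, it fits the wording and objective 1.2d, and it keeps about 60% power in the example. The loss arises only if three separate tests are meant.

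**Conclusion.** The concern holds as a small improvement at almost no cost. Section 11.3 leaves EFS and CR without the factors that balance randomisation. Taken as written, those comparisons are valid but slightly conservative: about 0 to 5 points of power for EFS, 1 point or less for CR, and an EFS hazard ratio attenuated by roughly 0.01 to 0.03 on the log scale. All of this rests on assumed stratum sizes and prognostic effects. A reader might infer a raised false-positive risk; the simulations show no clear inflation. A reader might also picture randomisation within three strata; Section 6.0 describes dynamic balancing on three factors, with 10 attainable combinations.

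For toxicity, the age stratification follows the stated objective and is not an error. What is missing is one sentence on how the age groups are combined. The two readings differ materially: 23%, 36% and 5% power separately against 60-64% combined, for 15% v 10% at the assumed group sizes.

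**What to change.** In Section 11.3:

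- **EFS:** compare arms by a Cox model and log-rank test stratified by the Section 6.0 factors.
- **CR:** use a Cochran-Mantel-Haenszel test on the same factors.
- **Sparse cells:** state in advance a rule for collapsing them, for example the adult RT-intent cells, and apply it to both endpoints.
- **Toxicity:** state that the age-stratified Fisher comparison is one combined exact conditional (or CMH) test with a common odds ratio, with rates shown by age group, and not three separate tests.

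The cost is a wording change, slightly more analysis work and some sparse cells to handle. The factors are already recorded for randomisation, so no new data are needed.

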### 1.2 Secondary Objectives:

- a. To compare overall survival (OS) in patients randomized to N-AVD versus BV-AVD.
- b. To compare event-free survival (EFS) in patients randomized to N-AVD versus BV-AVD.
- c. To compare the metabolic complete response (CR) rate at the end of treatment in patients randomized to N-AVD versus BV-AVD.
- d. To compare the physician-reported treatment-related adverse event rates between arms stratified by age groups.
- e. To compare patient-reported symptoms using selected PRO-CTCAE items between arms stratified by age groups.
- f. To compare the safety and tolerability of N-AVD versus that of BV-AVD.

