## 7.1 General Treatment Information

### a. Treatment Plan Overview

This is a multicenter, randomized, open-label Phase III clinical trial for participants with previously untreated advanced stage (III-IV) classical Hodgkin lymphoma.

Once a patient meets eligibility criteria, the patient will be randomized to either Arm 1 (N+AVD) or Arm 2 (BV+AVD).

The planned therapy duration is 6 x 28 day cycles, with study treatment administered on Days 1 and 15 of each cycle. See [Section 7.3](#) below for specific details about treatment regimen for each arm.

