NOTE: Unless indicated otherwise in the protocol, scheduled procedures and assessments (treatment administration, toxicity assessment for continuous treatment, disease assessment, specimen collection and follow-up activities) must follow the established SWOG guidelines as outlined in the SWOG Best Practices document accessible from the "Best Practices" link at: <https://www.swog.org/clinical-trials/protocol-workbench>.

- a PRO-CTCAE or Ped PRO-CTCAE questionnaire, based on patient age with adult  $\geq$  18 and pediatric 12-17 years, must be completed on Day 1, prior to beginning treatment (for English-, Spanish- and French-speaking adult and English-speaking pediatric patients). All subsequent PRO-CTCAE questionnaires must be completed within a +/- 7-day window of the indicated timepoint. See also [Section 15.6](#) for administration instructions.
- b For patients randomized to Arm 1 (N-AVD), TSH must be performed at baseline and then every 4-8 weeks prior to the start of the cycle, as clinically indicated. Results of the baseline TSH test does not determine eligibility but is performed prior to initiating treatment for Arm 1 patients only, in order to obtain baseline measurements.
- c Allowable window for CBC with differential is within 3 days prior to start of Cycles 1-6 and must include: WBC count, hemoglobin, absolute neutrophil count (ANC), and absolute lymphocyte count (ALC). See also [Section 7.1b](#) for extended allowable windows in event of COVID-19 extenuating circumstance.
- d Allowable window for CMP is within 3 days prior to start of Cycles 1-6 and must include: electrolytes (sodium, potassium, chloride, bicarbonate (CO2)), albumin, serum or plasma creatinine or calculated creatinine clearance, and liver function tests (total bilirubin, SGOT [AST], SGPT [ALT], alkaline phosphatase). See also [Section 7.1b](#) for extended allowable windows in event of COVID-19 extenuating circumstance.
- e Required within 6 months prior to registration for patients who are known to be HIV-positive.
- f A contrast-enhanced (diagnostic) CT, MRI or MR-PET is acceptable in event that PET-CT is contra-indicated, however if it is later possible to administer a PET-CT, then PET-CT is acceptable for the interim scan (after Cycle 2) (if performed) and the EOT assessment. Otherwise, if PET-CT is not subsequently possible, then the same modality as baseline must be used throughout the trial.

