- g For Patients Randomized to Arm1 (N-AVD): Recommended cardiac monitoring includes: EKG, ECHO, CPK & Troponins to be done within 3 days prior to Day 1 of each Cycle, as clinically indicated for patients who: 1) develop CHF, 2) are deemed at risk because of underlying cardiovascular disease or exposure to cardiotoxic drugs, or 3) have evidence of CHF or MI, cardiomyopathy, or myostis cardiac evaluation (NYHA I/II). See also [Section 7.3a](#).
- h See also: [Sections 14.4](#) and [15.4](#). NOTE: If patient goes off protocol treatment early the EOT PET-CT must still be collected/submitted at 4-8 wks after the last dose of study drug.
- i All pediatric patients and all patients who were declared (at date of registration) intent to treat with EOT Residual PET RT must have a standard of care PET-CT on Day 53 (+/-3 days) (after Cycle 2/Day 15 and prior to the start of Cycle 3).
- j 1 FFPE block or 1 H&E slide required per [Section 15.1](#) for pathology review. At same timepoint, with patient's consent, tissue must be collected for banking per [Section 15.2](#).
- k With patient's consent, peripheral blood must be collected per [Section 15.2](#).
- l Patient-reported outcome instruments are required at Baseline for patients who can complete the forms in English, Spanish, or French and must also be administered to these patients at the required follow-up time points (timing based on registration date). If a patient refuses or cannot complete the patient questionnaires at any time point, he or she should be asked to do so at the next scheduled assessment time. Note that there are two age-based versions of the PROMIS measures for adults 18+ and for pediatric patients age 12-17 years. See also [Sections 14.4](#) for data submission and [15.5](#) for administration instructions.
- m If patient goes on to receive RT, then toxicity and PRO-CTCAE assessments must be performed after administration of both the last dose of study drug and after last dose of radiation therapy.
- n End of treatment Residual PET RT is allowable for eligible patients, as indicated in [Section 7.5](#).
- o Females of childbearing potential who will receive radiation therapy per protocol must have a standard of care pregnancy test, prior to start of radiation therapy.
- p Targeted H&P with systems examined as per the treating physician discretion (must include weight).

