**CIRB Details**

#	Documents used for CIRB approval	Post Date
1	Consent Form (P/D 05/08/19): Spanish	20-Aug-2019
2	Protocol Version Date 05/08/19	19-Jul-2019
3	Consent Form (P/D 05/08/19)	19-Jul-2019

CIRB Documents	Supplemental Documents	Education and Promotion	Case Report Forms	Site Reg
Patient Enrollment	Adverse Event Reporting	Pharmacy	Remote Data Capture	Miscell

For assistance accessing information, refer to the [Accessibility Policy](#) to request reasonable accommodations.

Initial Reviews	Amendment Reviews	Continuing Reviews	Document Title	Post Date
Interim Guidance for COVID-19 Memorandum				
Correspondence			CIRB Acknowledgement of S1826 COVID19 Memo	16-Apr-2020
1			Memorandum - S1826 Protocol-Specific Interim Guidance for COVID-19 dated 05/01/20	16-Apr-2020
2				
Participant Materials				
CIRB Applications			CIRB Application (P/D 05/08/19)	21-Feb-2020
1				
Correspondence			CIRB Approval of Recruitment/Patient Education Materials (P/D 05/08/19) dated 02/14/20	21-Feb-2020
1				
Amendment Reviews				
1			Expedited Review Worksheet (P/D 05/08/19)	21-Feb-2020
Recruitment Material				
1				
2				
3				
			FACT/GOG-NTX Questionnaire Version 1.0	21-Feb-2020
			FACT/GOG-NTX Questionnaire Version 1.0 (French)	21-Feb-2020
			FACT/GOG-NTX Questionnaire Version 1.0 (Spanish)	21-Feb-2020

11. Where do I find the address for the SWOG Biospecimen Bank?

- Prior to shipment, all specimen must be entered into the SWOG online Specimen Tracking System.
- Log on to the SWOG Specimen Tracking System using your CTEP IAM username and password.
- If it is your first time logging in to the Specimen Tracking System (SpecTrack), please note that you can access start-up instructions (both written and demo) after signing into the online system.
- You will be able to print labels via the online SpecTrack system.

12. What Grade AEs do I need to report?
  - ALL adverse events are reported for both arms (for the duration of the reporting requirement).
13. For adverse event reporting, when Medidata Rave requests an answer to “attribution to study intervention,” how is that defined?
  - The attribution code indicates the likelihood that the condition/event observed is related to protocol treatment.
14. How do I clear the “sticky note” for the AE?

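### The only between-arm test named for clinician-graded toxicity counts events that unblinded sites attribute to treatment, and TSH testing is specified for Arm 1 only; an all-cause comparison should stand beside it

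*Combined protocol and SAP*

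**What the plan says.** Section 11.3 summarises toxicity in two ways. The maximum grade of each toxicity per patient goes into frequency tables, which are not limited to attributed events. The formal comparison is limited: "Treatment-related toxicities between arms will be compared using" Fisher's exact test, stratified by age group. It matches objective 1.2d: "To compare the physician-reported treatment-related adverse event rates between arms stratified by age groups". Objective 1.2f separately promises a comparison of safety and tolerability, but 11.3 names no all-cause between-arm test for it. No alpha or sidedness is given for the Fisher test.

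Section 7.1a states the design: "This is a multicenter, randomized, open-label Phase III clinical trial". Section 18.12b (question 13) explains attribution: "The attribution code indicates the likelihood that the condition/event observed is related to protocol treatment". No blinded or central review of attribution is described.

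On collection, Section 18.12b (question 12) says "ALL adverse events are reported for both arms", for as long as reporting is required. Section 14.4n narrows this in follow-up: a late Grade 3 or higher event is reported only if it is at least possibly related to protocol treatment, unless it is serious.

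On surveillance, Section 9.1 footnote b says of Arm 1 patients: "TSH must be performed at baseline and then every 4-8 weeks prior to the start of the cycle, as clinically indicated". It adds that the baseline test is for Arm 1 only. Footnote g, also addressed to Arm 1, begins: "Recommended cardiac monitoring includes: EKG, ECHO, CPK & Troponins". It is qualified as clinically indicated, for patients who develop heart failure, are judged at risk, or have cardiac findings. Blood counts and the metabolic panel are scheduled in both arms.

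**The concern.** An event enters the formal test only if it occurs, is detected and is attributed. Randomisation protects the first step, not the other two.

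**Attribution.** Sites know the arm, and the protocol directs their attention differently. Arm 1 has immune-toxicity tables and algorithms (8.2c, 18.3), and Arm 2 has its own neuropathy rules (8.2d). More ready attribution of immune-type events in Arm 1, or of neuropathy in Arm 2, is plausible. The direction can differ by event type, so a true difference can be inflated, masked or created.

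**Detection.** Section 2.4b reports endocrinopathy in 26% of N-AVD patients in one earlier cohort, all thyroid-related and Grade 1-2. Section 8.2c.2 anticipates asymptomatic hypothyroidism. Whether such events are recorded depends on whether someone tests, and the protocol asks for the test in one arm.

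At stake is how far the clinician-graded safety comparison can be read as a difference between drugs rather than between reporting practices.

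**Working it through.** **The plan's own figures.** Section 11.3 says that 470 patients per arm give toxicity rates to within 4.5 points. The half-width at a rate of 50% is 1.96 × √(0.5 × 0.5 / 470) = 0.0452, which agrees. It also claims at least a 90% chance of seeing a toxicity of 4% prevalence. 1 − 0.96^470 exceeds 0.9999, so the claim is true and very conservative. Neither figure bears on attribution or detection.

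**Inputs for the illustration.** From 11.3: 470 per arm and Fisher's exact test. Assumed: two-sided 5%, no stratification, the same true incidence in both arms, and every attribution and detection fraction below.

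**Formula.** The rate entering the test in arm i is p_i = incidence × fraction attributed (or detected). The rejection probability is the sum, over all counts x1 and x2 from 0 to 470, of Bin(x1; 470, p1) × Bin(x2; 470, p2) for those pairs with Fisher p ≤ 0.05.

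**Attribution.** One arm attributes 60%. At 30% incidence, for example, the rates are 0.30 × 0.60 = 18% against 0.30 × 0.70 = 21%.

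| True incidence | 60% vs 65% | 60% vs 70% | 60% vs 80% |
|---|---|---|---|
| 5% | 4% | 5% | 10% |
| 10% | 5% | 7% | 19% |
| 30% | 8% | 19% | 59% |
| 50% | 12% | 35% | 88% |

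With 60% attributed in both arms at incidences of 10% to 50%, the test rejects about 4% of the time, since Fisher's test is conservative. Starting from a higher base, 80% against 90% gives 7%, 11% and 23% at incidences of 10%, 20% and 40%.

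**Detection.** One arm detects every event, and the other detects 75% or 50%.

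| True incidence | 100% vs 75% | 100% vs 50% |
|---|---|---|
| 5% | 12% | 47% |
| 10% | 24% | 80% |
| 20% | 49% | 99% |

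Modest gaps matter little for uncommon events and considerably for common ones. The tables show sensitivity to a gap. They do not estimate one.

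**The case against.** Much of the case on the other side stands.

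- **Attribution is to the whole regimen.** Both arms contain doxorubicin, vinblastine and dacarbazine. A site coding neuropathy in Arm 1 already has vinblastine as a cause, and 8.2c.2 adjusts vinblastine for it. This narrows the likely attribution gap without closing it for events typical of one added drug. Nothing in the documents supports a gap as wide as 60% against 80%.
- **Safety data free of a relatedness filter are already planned.** The frequency tables are not restricted to related events, aggregate adverse event rates by arm are reviewed monthly (11.3), and the interim rule in 11.4 uses death or complete discontinuation due to an adverse event, without a relatedness condition. A reader might infer that the plan has no all-cause view of safety. It has one, but without a named between-arm comparison.
- **The treatment-related comparison is prespecified** by objective 1.2d and carries no decision or stopping role. It should stay.
- **Cardiac monitoring is not routine surveillance.** A reader might infer that cardiac enzymes are screened throughout Arm 1. Footnote g and Section 7.3a do not say so: the monitoring is recommended and depends on findings or risk. TSH after baseline also carries the clinically-indicated qualifier. The thyroid point keeps its force because TSH is specified for Arm 1 only.
- **The case for preferring a regimen does not turn on this test.** If PFS is similar, 2.5 rests that argument mainly on the quality-of-life studies. Their fatigue and neuropathy endpoints (18.2g) are patient-reported and have no attribution filter. PRO-CTCAE is also collected in both arms, but 18.10c calls its analysis exploratory.

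**Conclusion.** The point holds as a limited one. The named formal comparison of clinician-graded toxicity depends on unblinded attribution, and specified thyroid testing differs by arm, so part of an observed difference can come from either source. It rests on the open-label design, site-coded attribution, the wording of 11.3 and footnote b.

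The size is unknown. Under the assumed inputs, the false rejection rate ranges from near nominal (4% to 5% for a 5-point attribution gap at 10% incidence or less) to 59% or 88% for a 20-point gap at 30% or 50% incidence. These are illustrations only.

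A stronger conclusion, that the toxicity comparison is invalid or biased in a known direction, is not supported. The direction of attribution bias is not fixed, and the 26% figure comes from a single N-AVD cohort with no comparator. The primary endpoint, its error rate and the sample size are unaffected. The change is worth making because it is cheap and removes one avoidable source of bias.

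**What to change.** In Section 11.3:

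1. Add an age-stratified by-arm comparison of all-cause adverse events, using maximum grade per patient, over the treatment and reporting period in which all events are collected in both arms. State the alpha and sidedness.
2. Keep the treatment-related comparison beside it, serving objective 1.2d.
3. Report laboratory-detected thyroid events descriptively by arm and state that surveillance differed. Attach the same caveat to enzyme-detected cardiac events.
4. Do not add a formal test limited to symptomatic events. It would bring back unblinded judgement, and the documents show no symptomatic flag being collected.

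**Cost.** One additional table from data already collected for that period, with no change to monitoring, patient management or sample size. All-cause rates include disease-related events and are noisier. The comparison cannot extend to late follow-up, because 14.4n collects non-serious Grade 3 or higher events there only if attributed. Nor does it correct unequal detection, which is why item 3 is needed.
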